12.1 Responsibilities

The Chief Investigator is responsible for forwarding the following documents to the study sponsor for review before study initiation from the sponsor can occur:

- Signed and dated protocol signature page (see Investigator's Agreement on page 3)
- Copy of local research and development office and site specific assessment approvals, or equivalents thereof.

- Copy of approved patient information sheet and informed consent form on headed paper which will be used at the site
- Up-to-date *curricula vitae* of the Principal Investigator (hand-signed and hand-dated within 1 year)
- GCP training certificate (which must be within 3 years)
- Contact details for key study personnel and completed, signed site delegation log
- Signed study contract/ HRA statement of activities

Delegation logs will be kept which outline the allocation of responsibilities following adequate training: patients enrolment, monitoring study progress, the day-to-day running of the study, data collection, Case Report Forms, consent forms, data analysis, and data storage.

Specimen collection will be performed by staff trained/experienced in the collection as per standard of care. This will not necessarily be a member of the study team. The study team will ensure the samples are anonymised prior to being sent for analysis.

Transportation and storage will be arranged by a dedicated Translational team in the GI & Lymphoma Unit. Members of the team are GCP and IATA trained and certificates are available for review.

12.2 Start date

The study is reviewed and approved by the Committee for Clinical Research (CCR) only (as sponsor) prior to external regulatory review. Once REC/HRA review and approval is gained local R&D confirmation of capacity and capability is required before the study can start at a participating site.

12.3 Patient screening and enrolment

Patients will be considered as enrolled in the study after informed consent and registration has occurred. Any health care professional with GCP training who has been delegated by the Principal Investigator can obtain consent from eligible patients. At registration, each patient will be assigned a study subject identification number which will be used to identify the patient.

Before patients may be enrolled into the trial, the sponsor must receive proof that all required regulatory approval (both local and, if relevant, national) has been obtained for the site.

Before registration, each potential patient must be given a patient information sheet, and informed consent obtained according to the requirements of GCP. The registration case report forms (CRFs) must also be completed. Only patients fulfilling all inclusion criteria and not any exclusion criteria should be registered. Any queries about eligibility should be addressed directly with the clinical team.

A study subject identification number will be issued initially to the patient by the healthcare professional performing the patient registration – instructions will be provided separately. Once eligibility has been reviewed and the researcher is satisfied that the patient meets the criteria for study registration the subject identification number will be assigned to the patient. Completed registration CRFs must be sent to the GI & Lymphoma Trials Office at the Royal Marsden Hospital. The GI & Lymphoma Trials Office will check for completeness, complete the relevant CRF page and send back to the study personnel at the participating site responsible for recruitment of the patient.

12.4 Patient withdrawal

Withdrawal of full consent for a study means that the patient does not wish to or is unable to continue further study participation. Any patient may withdraw full consent to participate in the study at any time during the study. The investigator will discuss with the patient the most appropriate way to withdraw to maintain the patient's care. In this case, the patient's data already collected up to the point of withdrawal will still be included in the analysis of data, and the patient censored from that point onwards.

Withdrawal of partial consent means that the patient does not wish to undergo any further procedures (e.g. blood tests or swabs) but is still willing to collaborate in providing further data by continuing on study (e.g. permit further data collection from hospital records). Participants will have the opportunity to request for their samples to be discarded.

12.5 Study duration

The study is expected to take up to 6-9 months to complete accrual. If the recruitment target is reached before the predicted end date, then the trial will close early to any further recruitment. Conversely, if the target recruitment is not achieved by the estimated end date, the trial recruitment

period may be extended until the target number of patients is achieved depending on the overall status of the SARS-CoV-2 pandemic.

Individual participants whose throat/nose swab RT-PCR does not confirm SARS-CoV-2 infection and do not have a high clinical suspicion of SARS-CoV-2 infection at D0 will come off study at this time and no further clinical data or samples will be collected. Research samples will be destroyed. This only applies to Arm A.

12.6 End of study

The 'end of study' will be defined as the date that the last patient has had their last visit, or when adequate follow up has occurred for all the study end points to assessed and reported, whichever is sooner. At this point, the 'end of trial notification' will be submitted to the relevant regulatory authorities and ethics committees.

13. Safety reporting

The risks of an adverse event related to study specify procedures have been deemed to be minimal. Therefore, any AEs arising from the study procedures will not be recorded for the purposes of this study.

14. Evaluation of Outcome/Statistical Considerations

14.1 Sample size

Arm A

Based upon the current SARS-CoV-2 infection rates at the Royal Marsden NHS Foundation Trust, up to 60 patients (up to 50 patients with solid tumour or 10 with lymphoma) with confirmed SARS-CoV-2 infection by RT-PCR could be recruited in 6-9 months, assuming uptake of 40% (As per positivity rates in April 2020) in screening 150 patients.

For the primary endpoint, seroconversion, and the RT-PCR and LFA viral clearance secondary endpoints:

Arm A - Up to 60 SARS-CoV-2 positive patients are expected to be recruited in the study; the proportion of patients can be estimated with a 95% CI with a width of ±12.7%. In the 50 patient solid tumour cohort then this will be estimated with a 95% CI with a width of ±13.9%.

To account for lower recruitment rate of SARS-CoV-2 positive patients, the following table presents the maximum width of the 95% C.I.s, given a 50% observed proportion for the primary endpoint, according to different sample sizes (N).

An observed proportion of 50% has been selected, which is conservative and gives the widest possible 95% CI. (Table 4)

Table 4:

N	Proportion of patients, with a positive detection of IgM and IgG specific antibodies to SARS-CoV-2.	With of 95% CI
10	50%	± 31.0%
20	50%	± 21.9%
30	50%	± 17.9%
50	50%	± 13.9%
60	50%	± 12.7%

Arm B

For the primary endpoint up to 150 patients are expected to be recruited in Arm B. Considering a 10% antibody positivity rate [10], the proportion of patients can be estimated with a 95% CI with a width of ± 4.8%.

The clinical course of SARS-CoV-2 infection secondary endpoint is descriptive so no power calculation is required.

Due to the dynamic changes in the prevalence of SARS-CoV-2 infection during the pandemic, the study may be halted prematurely.

14.2 Analysis plan

The primary endpoint will be presented as the proportion of patients at each sample time-point with 95% confidence interval Arms A and B will be reported separately.

Continuous data will be summarised as n, mean, standard deviation, median, minimum value and maximum value. Categorical data will be presented as frequencies and percentages.

Arm A:

The secondary endpoint, viral clearance, will be presented as the proportion of patients at each sample time-point with 95% confidence interval.

The clinical course of SARS-CoV-2 infection described as patient characteristics, and cancer diagnosis, will be summarised, as well as duration and severity of clinical symptoms, supportive treatments given, cancer treatments received and outcome of SARS-CoV-2 infection.

Feasibility of SARS-CoV-2 antigen testing with a lateral flow assay will be assessed by the following

- 1 Proportion of samples successfully processed and result obtained, with 95% confidence interval
- 2 Proportion of samples processed with a positive result by lateral flow, by the gold standard (throat/nose RT-PCR)

Arm B:

Feasibility of SARS-CoV-2 antibody testing with a lateral flow assay will be assessed by the following

- 1 Proportion of samples successfully processed and result obtained, with 95% confidence interval
- 2 Proportion of samples processed with a positive result by lateral flow, by the gold standard (SARS-CoV-2 laboratory serology test)

The formal statistical analysis plan will be developed based on the size of the available cohort and the performance of the experiment assays. The analysis will be developed in a separate molecular and statistical analysis plan which will be drafted and approved by the Trial Management Group (TMG) with statistical input. However, the above gives a guide as to the planned analyses.

14.3 Study monitoring

The study will be centrally monitored using the following procedures:

Central Eligibility checking at registration

Registration eligibility criteria will be reviewed when CRFs are received by the GI & Lymphoma Trials Office. Registration will only take place once central checking of documents is complete and any queries addressed.

Statistical Monitoring

The trial statistician will regularly examine the data for anomalies and outliers, such as too few or too many events. Queries will be raised by the trial coordinators (or other appropriately delegated team member) in such situations and communication with the clinical teams will take place. In addition statistical monitoring of unusual dates and inconsistent data will take place. Again these will raise queries via the trial coordinators (or other appropriately delegated team members.)

RM GI Unit Research Meetings

Recruitment will be discussed in the Unit Research meetings.

Trial Management Group (TMG) meetings

The role of the Trial Management Group (TMG) is to monitor all the aspects of the conduct and progress of the study, ensuring that the protocol is adhered to. The TMG will develop and approve the molecular analysis plan. Any issues will be raised and addressed at the TMG meetings. The TMG will meet at minimum frequency of every 3 months. The minutes of the meeting will be documented in the Trial Master File (TMF) and copied to the Sponsor.

15. Regulatory & Ethics Committee Approval

15.1 Ethical considerations

Ethical considerations relating to this trial will be carried out in accordance to the Declaration of Helsinki (1996).

A copy of the protocol, proposed informed consent form, other written patient information, and any proposed advertising material must be submitted to an independent ethics committee and any other relevant regulatory authorities, subject to the regulations of the country of each participating site, for written approval. A copy of the written approval of the protocol and informed consent form must be received by the sponsor before recruitment of patients into the study.

The investigator must submit and, where necessary, obtain approval from the independent ethics committee concerned and any other relevant regulatory authorities for all subsequent protocol amendments and changes to the informed consent document. The investigator should notify the same of deviations from the protocol.

15.2 Informed consent

Before a patient's participation in the clinical study, the investigator (or a member of the study team named in the site signature log and authorised by the site Principal Investigator) is responsible for obtaining written informed consent from the patient. This can only take place after the patient has been given adequate time to consider participation, and adequate explanation of the aims, methods, anticipated benefits, and potential hazards of the study, and must take place prior to any protocol-specific procedures.

The acquisition of informed consent should be documented in the patient's medical records, and the informed consent form should be signed and personally dated by the patient and by the authorised person who conducted the informed consent discussion. The original signed informed consent form should be retained in accordance with institutional policy and GCP, and a copy of the signed consent form should be provided to the patient or consultee.

If a potential patient is illiterate or visually impaired and does not have a consultee, the investigator must provide an impartial witness to read the informed consent form to the patient and must allow for questions. Thereafter, both the patient and the witness must sign the informed consent form to attest that informed consent was freely given and understood.

In the event a study participant loses capacity to provide ongoing consent (e.g. due to medical illness), ongoing participation will be discussed with the participant's consultee. The consultee will be provided with the Consultee information sheet and, if in agreement, provide written confirmation for continued study participation on the consultee declaration form. Withdrawal from the study will also be considered if ongoing participation is not believed to be in the patient's best interests.

15.3 Patient confidentiality

The investigator must ensure that the patient's confidentiality is maintained in compliance with the UK Data Protection Act of 2018 and the General Data Protection Regulation (GDPR). On the case report forms or other documents submitted to the sponsor, patients should be identified by their initials and a patient study subject identification number only. Documents that are not for

submission to the Sponsor (e.g., signed informed consent forms) should be kept in strict confidence by the Investigator.

16. Data Handling and Record Keeping

16.1 Investigator Signatory Obligations

Each clinical study report or case report form should be signed by the investigator or a member of the study team named in the site signature log and authorised by the site principal investigator.

Original copies of all completed case report forms should be retained by the site once they have been emailed to the GI & Lymphoma Trials Unit.

16.2 Data Handling

In compliance with GCP guidelines, it is required that the investigator and institution permit authorised representatives of the sponsor and of the regulatory agency(s) direct access to review the patient's original medical records for verification of study-related procedures and data. Direct access includes examining, analysing, verifying, and reproducing any records and reports that are important to the evaluation of the study. The investigator is obligated to inform and obtain the consent of the patient to permit named representatives to have access to his/her study-related records without violating the confidentiality of the patient.

In this study anonymisation will be carried out by allocating a study subject identification number for samples which will be linked with a study subject identification number for patient outcome data, all patient identifiers will be removed. Tissue samples will be coded on entry to the study so that in all circumstances researchers carrying out the analysis will not have access to details that identify the patient and will see all data in an anonymised form.

Clinical data will be entered on to a MACRO database, which is held within a password protected environment with access controlled.

16.3 Study Documentation and Archive

The investigator should maintain a list of appropriately qualified persons to whom he/she has delegated study duties. All persons authorised to make entries and/or corrections on case report forms will be included on the site signature log.

Source documents are original documents, data, and records from which the patient's Case Report Form data are obtained. These include but are not limited to hospital records, clinical and office charts, laboratory and pharmacy records, diaries, radiographs, and correspondence. The investigator and study staff are responsible for maintaining a comprehensive and centralised filing system of all study-related (essential) documentation, suitable for inspection at any time by representatives from the sponsor and/or applicable regulatory authorities. Elements should include:

- Patient files containing completed case report forms, informed consent forms, and patient identification list
- Study files containing the protocol with all amendments, copies of pre-study documentation, and all correspondence to and from the sponsor and institutional review board.

In addition, all original source documents supporting entries in the case report forms must be maintained and be readily available to permit trial related monitoring, audits, REC review and regulatory inspections where appropriate.

No study document should be destroyed without prior written agreement between the sponsor and the investigator. Should the investigator wish to assign the study records to another party or move them to another location, he/she must notify the sponsor in writing of the new responsible person and/or the new location.

Sponsor should ensure that all trial related documentation be retained for maximum period of time as specified in the UK clinical trials regulations.

16.4 Quality assurance/audit

Systems of quality assurance, including all elements described in this protocol will be implemented. Quality control is applied to each stage of data handling to ensure that data is accurate, reliable and processed correctly. All data and documentation related to this study will be available for GCP audit. All research staff will assist in all aspects of audit/inspection.

16.5 Annual reporting to REC

An Annual Progress Report will be submitted to the Research Committee.

16.6 Sample labelling, storage and destruction

In order to protect patient identity all samples will not be labelled with any information that may lead to the direct identification of the patient concerned, including patient name, date of birth, National Health Service (NHS) or hospital number. Instead, tissue and other specimens from each patient will be labelled with the study name, the study subject identification number (assigned at registration) and initials.

Samples will be stored indefinitely in secure facilities at St George's University Hospitals NHS Foundation Trust and offsite approved storage facilities (UK). However, the patient retains the right to have the sample material destroyed at any time.

The sponsor will be the exclusive owner of any data, discoveries, or derivative materials from the sample materials and is responsible, via the Chief Investigator, for the destruction of the sample(s) at the request of the research patient.

16.7 Use of information

All unpublished information relating to this study is considered confidential.

17. Financing, Indemnity & Insurance

The study sponsor is the Royal Marsden NHS Foundation Trust, [name], United Kingdom. This study has been financed by the Royal Marsden Cancer Charity and the NIHR Biomedical Research Centre. Material Transfer Agreements (MTA) will be executed with St Georges Hospital.

No specific compensation arrangement exists for harmful events which might arise from participation in the study. However, the study is covered for negligent claims occurring with the NHS

by Crown indemnity. There is no pre-existing arrangement for non-negligent claims arising from the conduct of the study.

18. Publication Policy

The investigators will co-ordinate publication strategies, presentations and peer review publication. Authorship of any publications resulting from this study will be determined on the basis of the Uniform Requirement for Manuscripts Submitted to Biomedical Journals (International Committee of Medical Journal Editors, 2005), which states:

- Authorship credit should be based on (1) substantial contributions to conception and design, acquisition of data, or analysis and interpretation of data; (2) drafting the article or revising it critically for important intellectual content; (3) final approval of the version to be published. Authors should meet conditions 1, 2, and 3.
- When a large, multicentre group has conducted the work, the group should identify the individuals who accept direct responsibility for the manuscript. These individuals should fully meet the criteria for authorship defined above.
- Acquisition of funding, collection of data, or general supervision of the research group, alone, does not justify authorship.
- All persons designated as authors should qualify for authorship, and all those who qualify should be listed.
- Each author should have participated sufficiently in the work to take public responsibility for appropriate portions of the content.

19. Abbreviations

ACE2	Angiotensin-Converting Enzyme 2
ARDS	Acute respiratory distress syndrome
ASCs	Antibody-Secreting Cells
CI	Confidence Interval
COVID-19	Coronavirus Disease 2019

CRF	Case Report Form
CRP	C-reactive Protein
D	Day number
DFID	Department for International Development
EDTA	Ethylenediaminetetraacetic Acid
ELISA	Enzyme-Linked Immunosorbent Assay
GCP	Good Clinical Practice
GP	General Practitioner
IL	interleukin

RT-PCR	Reverse Transcription-Polymerase Chain Reaction
SAP	Statistical Analysis Plan
SARS	Severe acute respiratory syndrome
SD	Standard deviation
SUSAR	Suspected unexpected serious adverse reaction
TMG	Trial management group

Amendment history

Date	Version	Timing in relation to analysis	Brief description of change	Justification for change
09.12.2021	1.0	First version prior to the final analysis	N/A	N/A

1. Study Summary

CARDS is an observational study which will investigate how host cancer status and immune phenotype links to SARS-CoV-2 infection clinical presentation, seroconversion, and viral clearance. The study will also evaluate rapid antigen/antibody lateral flow tests.

2. Study objectives

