12. Study Organisation/ Trial Monitoring and Management Strategy	27
12.1 Responsibilities	27
12.2 Start date	28
12.3 Patient screening and enrolment	28
12.4 Patient withdrawal.....	29
12.5 Study duration	29
12.6 End of study	30

13. Safety reporting	30
14. Evaluation of Outcome/Statistical Considerations	30
14.1 Sample size.....	30
14.2 Analysis plan	31
14.3 Study monitoring	32
15. Regulatory & Ethics Committee Approval	33
15.1 Ethical considerations.....	33
15.2 Informed consent.....	34
15.3 Patient confidentiality.....	34
16. Data Handling and Record Keeping	35
16.1 Investigator Signatory Obligations.....	35
16.2 Data Handling.....	35
16.3 Study Documentation and Archive	36
16.4 Quality assurance/audit.....	36
16.5 Annual reporting to REC	37
16.6 Sample labelling, storage and destruction	37
16.7 Use of information	37
17. Financing, Indemnity & Insurance	37
18. Publication Policy	38
19. Abbreviations	38
20. Protocol Summary of Changes.....	40
21. References	41

1. Protocol synopsis

Study title: Cancer: Rapid Diagnostics and Immune assessment for SARS-CoV-2

Chief investigator: [name]

Study centres: The Royal Marsden NHS Foundation Trust

Study period: Approximately 1 year

Follow up duration: Up to 84 days

Main objective: This observational study will investigate how host cancer status and immune phenotype links to SARS-CoV-2 infection clinical presentation, seroconversion, and viral clearance. The study will also evaluate rapid antigen/antibody lateral flow tests.

Methodology: Arm A: Suspected acute COVID-19 infection

Throat/nose swabs, saliva and blood will be collected from patients undergoing investigation for suspected SARS-CoV-2 infection at the Royal Marsden NHS Foundation Trust on Day 0. Patients who are positive for SARS-CoV-2 by throat/nose RT-PCR or have a high clinical suspicion for acute COVID-19 will have further samples collected on D7 (if an inpatient), D14, D28, D42 and D56.

Arm B: Asymptomatic patients with no clinical suspicion of COVID-19

Blood will be collected from patients who do not have symptoms of COVID-19. Repeat blood will be collected on D28, D56 and D84.

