8.1 Number of patients

Arm A: Up to 60 patients with solid tumour malignancy or lymphoma with confirmed diagnosis of SARS-CoV-2 by RT-PCR will be recruited over the study period.

Arm B: Up to 150 patients with solid tumour malignancy or lymphoma with no clinical suspicion of COVID-19

Patients will be recruited from the Royal Marsden NHS Foundation Trust in both the inpatient and outpatient setting.

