5.2 Baseline patient characteristics

Patients will be described with respect to age, gender, cancer stage at diagnosis, anatomical site of malignancy, etc. Categorical data will be summarised by numbers and percentages. Continuous data will be summarised by mean, SD and range if data are normal and median, IQR and range if data are skewed. Minimum and maximum values will also be presented for continuous data.

6. Definitions of endpoints for analysis

Given that only one patient was recruited into Arm A, no analysis will be conducted on Arm A patients and all subsequent sections will refer to Arm B patients.

Pseudovirus neutralisation results are provided as continuous values, and currently there is limited research suggesting where the cut-off should lie in order to dichotomise the measurements into positive\negative neutralisation. Based on preliminary exploratory analysis run by the lab team at St. George's Hospital, we will dichotomise the pseudovirus neutralisation results using two different cut-offs: 0.5 and 0.8. Any endpoint involving pseudovirus neutralisation will be reported using each different cut-off.

Descriptive analysis on pseudovirus neutralisation results (summary statistics and boxplot by timepoint) will be included in the report.

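### Two objectives that the SAP keeps, on host cancer status and on systemic therapy, have no analysis in Arm B, and SAP 11 does not declare either withdrawn

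*SAP*

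**What the plan says.** **Objectives.** The protocol synopsis opens its objective with "Main objective: This observational study will investigate how host cancer status and immune phenotype links to SARS-CoV-2 infection clinical presentation, seroconversion, and viral clearance", and SAP 1 repeats it, describing an observational study "which will investigate how host cancer status and immune phenotype links to SARS-CoV-2 infection clinical presentation, seroconversion, and viral clearance". For Arm B, Protocol 6 and SAP 2.2 add two aims: antibody prevalence in patients with cancer, and the effect of systemic therapy on titres. Protocol 5 turns the second into a hypothesis, that systemic treatment lowers antibody levels.

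**Who is in Arm B.** Protocol 8.1 allows "Up to 150 patients with solid tumour malignancy or lymphoma with no clinical suspicion of COVID-19", with no quota by disease.

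**What is analysed.** SAP 6 states: "Given that only one patient was recruited into Arm A, no analysis will be conducted on Arm A patients". The Arm B populations in SAP 4.3 are all patients with a blood test, unvaccinated, vaccinated, and vaccinated with a second dose. The proportions in SAP 7.1 to 7.3 are broken down by timepoint or days since first vaccine, vaccination status, earlier nucleocapsid result, or agreement with the pseudovirus assay. Cancer variables appear once, in SAP 5.2: "Patients will be described with respect to age, gender, cancer stage at diagnosis, anatomical site of malignancy, etc".

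**What is declared as changed.** SAP 11 lists five items: Arm A excluded, IgM dropped, pseudovirus results used in place of lateral flow, vaccination status taken into account, and the exploratory endpoints dropped. Neither cancer status nor systemic therapy is named.

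**The concern.** Every participant has cancer and there is no cancer-free comparison group, so cancer status can be studied only by contrasts within the cohort: tumour type, stage or treatment. The SAP plans none of these. A report that follows it would restate both objectives and present nothing on either, without telling the reader that they had been set aside.

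A subgroup view chosen after the data have been seen would carry less weight than one named now. The SAP is dated before the final analysis, so naming it costs little.

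**Working it through.** **1. Objective against analysis**

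| Objective kept in the SAP | Variable needed | Where it is used | Withdrawn in SAP 11? |
|---|---|---|---|
| Cancer status and seroconversion (SAP 1) | Tumour type, stage or treatment | Stage and site in the baseline table only (5.2) | No |
| Systemic therapy and titres (SAP 2.2) | Treatment | Not used | No |
| Antibody prevalence in patients with cancer (SAP 2.2) | None beyond cohort membership | 7.1 and 7.2 | Not applicable; it is analysed |

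**2. The plan's own precision figures reproduce.** The half-width is 1.96 × √(p(1−p)/N).
- Arm B, N = 150, p = 0.10: 1.96 × √(0.09/150) = 4.8 points (stated ±4.8%).
- Arm A, N = 60, p = 0.50: 12.65 points (stated ±12.7%).
- Arm A solid tumour, N = 50, p = 0.50: 13.86 points (stated ±13.9%).

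The last is the only disease-specific estimate in either document. It belongs to Arm A, for which Protocol 14.1 planned "up to 50 patients with solid tumour or 10 with lymphoma", and it lapsed with that arm.

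**3. How far the pooled proportion depends on the mix.** With lymphoma share w, pooled = (1−w) × p(solid) + w × p(lymphoma). A share of 1/6 is the Arm A plan (10 of 60). The 40% share and all rates by disease are assumptions.

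| p(solid) | p(lymphoma) | w = 1/6 | w = 40% | Shift |
|---|---|---|---|---|
| any | equal | same | same | 0 |
| 10% | 5% | 9.2% | 8.0% | 1.2 points |
| 90% | 60% | 85.0% | 78.0% | 7.0 points |
| 90% | 40% | 81.7% | 70.0% | 11.7 points |

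The 10% is the protocol's planning rate for Arm B. At that level the shift is well inside the planned ±4.8 points. The larger shifts need high positivity, such as might follow vaccination, together with a large difference between diseases.

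**4. What reporting by disease would deliver.** Apply the 1/6 share to the ceiling of 150: 150 × 1/6 = 25 lymphoma and 125 solid tumour. The half-widths at p = 0.10 are ±11.8 points (lymphoma) and ±5.3 (solid tumour); at p = 0.50 they are ±19.6 and ±8.8.

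The next table gives exact (Clopper-Pearson) 95% intervals, the type the SAP specifies, for assumed rates near 50% and 90% within a vaccinated subset of varying size.

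| Vaccinated share of 150 (assumed) | Lymphoma | Solid tumour | Intervals |
|---|---|---|---|
| All | 13/25: 31-72% | 112/125: 83-94% | Separate |
| About half | 6/12: 21-79% | 56/62: 80-96% | Barely separate |
| About one third | 4/8: 16-84% | 38/42: 77-97% | Overlap |

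**5. Are the data there?** Protocol 11.1 collects medical history, including malignancy and its treatment, and concomitant medications at baseline in both arms. The Arm B schedule (Protocol Table 3) lists concomitant medications at D0 only, so therapy status is directly available at baseline. Later changes would have to come from the electronic records that Protocol 10 allows as a supplement.

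**The case against.** **SAP 1 is carried-over text.** The same short section still promises immune phenotype, viral clearance and lateral flow evaluation, all of which the SAP drops or replaces elsewhere. SAP 6.3.3 and 11 also say that the focus has moved to serological responses to infection and vaccination. This stands in part: cancer status may survive in SAP 1 by oversight. But the shift is given as the reason for dropping the exploratory endpoints, and it names neither objective. SAP 2.2, which is specific to the arm still being analysed, keeps the therapy objective.

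**The wording leans towards Arm A.** Infection presentation and viral clearance are Arm A matters, and the Arm A hypothesis is the one about seroconversion. However, Protocol 7.1 uses seroconversion for both arms.

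**Solid tumour versus lymphoma is one reading.** Cancer status is never defined. This stands. The disease split is the one that the protocol used for Arm A precision; the contrast that the documents name for Arm B is systemic therapy. Hence both belong in the remedy.

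**Stronger readings that do not hold.** A reader might infer that the pooled proportions are invalid or describe nobody. The stated aim is prevalence in patients with cancer, which is by nature a mixture, and SAP 5.2 reports site, so the mix should be largely visible. A reader might also infer that losing Arm A caused the pooling; Arm B was always one cohort with one pooled sample-size estimate (Protocol 8.1 and 14.1), and the protocol's analysis plan (14.2) has no disease split. Nor do the documents show that the mix drives the result, or that the two disease groups would separate clearly. The first needs rates they do not give; the second holds only when nearly all 150 patients fall in the same analysis set.

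**Conclusion.** The point holds as a gap between stated objectives and planned analyses. Two objectives that the SAP retains have no analysis on any reading of cancer status, and their loss is not declared. No figure in the plan is wrong, and the pooled estimates stand for the cohort enrolled.

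The numerical effect of disease mix cannot be known from the documents. It is nil if rates are equal, and otherwise about 1 point to about 12 points over the assumptions shown. The case for change rests on the unanswered objectives and not on that range. It is a modest point, worth correcting because the correction is cheap.

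**What to change.** **Preferred.** In SAP 7.1 and 7.2, add that the antibody proportions, and the neutralisation proportions where already planned, will be reported overall and also (a) by solid tumour versus lymphoma and (b) by systemic therapy status. Give counts and exact two-sided 95% intervals, and state that this is descriptive, with no testing, as SAP 4.1 requires. Define therapy status in advance from the baseline history, including how patients who have only planned treatment are classed. The therapy objective is phrased in titres, so proportions answer it only in part; the SAP should say so.

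**Otherwise.** State in SAP 1 and 2.2 that the two objectives are not addressed, and add both to the list in SAP 11.

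**Cost.** The preferred route needs a few lines of SAP text and extra table columns, using history already collected at baseline. The intervals will be wide in the smaller groups, most of all for lymphoma within vaccination subsets, and the groups may not separate. The report should say that overlapping intervals there are not evidence of similar rates. The alternative costs only wording, but leaves the questions unanswered.
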